## 10. SCHEDULE OF STUDY PROCEDURES

Study procedures are summarized across all study visits within the schedule of assessments (Table 9-1). Both Parts 1 and 2 of the study will follow the same study schedule, except where noted below.

### 10.1. Screening

Patients should be screened no more than 14 days before the first dose of study treatment is administered. Written informed consent must be obtained from each patient before the initiation of any screening procedures. Informed consent and brain scans may be obtained up to 28 days prior to the first study treatment administration. After a patient has given informed consent, eligibility will be determined by a review of the inclusion/exclusion criteria and completion of all screening procedures outlined in Table 9-1 and listed below.

- Collection of demographics
- Collection of medical history
- ECOG performance status evaluation
- Physical examination
- Height, weight, and vital signs measurements
- Clinical chemistry, hematology, and urinalysis tests
- Electrocardiogram
- Pregnancy test
- Tumor assessment (by CT scan or MRI; see details in Section 11.5.1); CT or MRI scans obtained prior to informed consent will not need to be repeated if performed within 14 days prior to dosing.
- Brain scan with contrast (by MRI or CT); brain MRI or CT scans obtained prior to informed consent will not need to be repeated if performed within 28 days prior to dosing.

Adverse events and concomitant medications will be monitored continuously from the time of informed consent through the Post-Treatment Visit.

### 10.2. Enrollment

Eligibility will be determined prior to enrollment, randomization (Part 2), and the start of study treatment. Eligible patients will be instructed on all protocol requirements, including any restrictions on concomitant medication usage.

For Part 2 of the study, randomization will be performed within 3 days of the first dose of G1T28 or placebo + E/P chemotherapy, following confirmation that the patient is eligible for the study.

Archived tumor samples must be sent to a central pathology laboratory to confirm the diagnosis of SCLC. Available tissue after confirming the diagnosis of SCLC will be banked for assessment of relevant DNA, RNA, and protein markers, such as those involved in the CDK4/6 pathway (see Section 11.4). This should be done as soon as possible after a patient

has enrolled in the study. If central pathology review does not confirm SCLC diagnosis, the patient may be withdrawn from the study after consultation between the principal investigator, medical monitor, and sponsor. For additional guidance regarding the shipment of samples to the central pathology laboratory, please refer to the Laboratory Manual.

### 10.3. Cycle 1

Adverse events and concomitant medications will be monitored throughout the study. Safety surveillance reporting of AEs commences at the time informed consent and continues through the Post-Treatment Visit.

#### Cycle 1 Day 1

Enrolled patients will return to the study center on study Day 1. The following procedures will be performed and results reviewed before study drug administration:

- ECOG performance status evaluation
- Physical examination
- Weight and vital signs measurements
- Clinical chemistry, hematology, and urinalysis tests (note: clinical chemistry and urinalysis tests may be obtained up to 72 hours prior to the first dose of each cycle of study treatments, and hematology tests may be obtained up to 24 hours prior to the first dose of each cycle of study treatments). **For the Phase 1b dose-finding portion of Part 1, Cycle 1 only**, the clinical chemistry and hematology results may be reviewed prior to or after dosing, depending on the availability of the lab report. For Day 1 of all subsequent cycles, the clinical chemistry and hematology results should be reviewed before dosing.
- Electrocardiogram (as applicable and optional after Cohort 1, predose, **Cycle 1 in the Phase 1b dose-finding portion of Part 1 only**)
- Plasma PK sample (as applicable and optional after Cohort 1, predose, **Cycle 1 in the Phase 1b dose-finding portion of Part 1 only**)
- Pregnancy test (note: may be obtained up to 72 hours prior to the first dose of each cycle)
- Functional Assessment of Cancer Therapy – Lung quality of life (QOL) instrument (FACT-L) and Functional Assessment of Cancer Therapy –Anemia QOL instrument (FACT-An) Questionnaires
- Immunologic marker blood sample collection (predose, **Part 2 only**)

The timing for critical assessments/procedures is outlined in [Table 9-1](#).

Patients that still meet all of the eligibility criteria will begin treatment Cycle 1. The first dose of study treatments (G1T28 or placebo + E/P chemotherapy) will be administered (as described in Section [8.1](#)) and all Day 1 postdose procedures outlined in [Table 9-1](#) will be completed. Postdose assessments on Day 1 are as follows:

- Vital signs (obtained immediately before and after G1T28 or placebo infusion, and etoposide and carboplatin infusions; only needed once between infusions)
- Electrocardiogram (as applicable, end of infusion [EOI] of G1T28, 2 hours ( $\pm 10$  minutes) after the start of G1T28, and 6.5 hours ( $\pm 15$  minutes) after the start of

G1T28, **Cycle 1 in the Phase 1b dose-finding portion of Part 1 only**). The 2-hour ECG will be completed once the etoposide infusion is complete.

- Plasma PK samples (as applicable and optional after Cohort 1, postdose samples as described in Section 11.2, **Cycle 1 in the Phase 1b dose-finding portion of Part 1 only**)

#### Cycle 1 Days 2, 3, 8, 10, and 15

All procedures and assessments to be conducted during Cycle 1 Days 2, 3, 8, 10, and 15 are outlined in Table 9-1. The DMC may recommend decreasing the frequency of hematological evaluations based on accumulating data. The investigators and institutional review boards (IRBs) will be notified if the frequency is reduced.

At Day 2 and Day 3, study treatments (G1T28 or placebo + etoposide) will be administered (as described in Section 8.1).

At Day 3 in Cycle 1 of the Phase 1b dose-finding portion of Part 1 only, the following additional assessments will be performed:

- Electrocardiogram (as applicable, predose, EOI, and 2 hours ( $\pm$  10 minutes) and 6.5 hours ( $\pm$  15 minutes) after the start of G1T28)
- Plasma PK sample (as applicable and optional after Cohort 1, predose and postdose samples as described in Section 11.2)

#### **10.4. Cycle 2**

Adverse events and concomitant medications will be monitored throughout the study. Safety surveillance reporting of AEs commences at the time of informed consent and continues through the Post-Treatment Visit.

#### Cycle 2 Day 1

Patients will return to the study center on Cycle 2 Day 1. The following procedures will be performed and results reviewed before study drug administration:

- ECOG performance status evaluation
- Physical examination
- Weight and vital signs measurements (calculate BSA)
- Clinical chemistry, hematology, and urinalysis tests (note: clinical chemistry and urinalysis tests may be obtained up to 72 hours prior to the first dose of each cycle of study treatments, and hematology tests may be obtained up to 24 hours prior to the first dose of each cycle of study treatments)
- Pregnancy test (note: may be obtained up to 72 hours prior to the first dose of each cycle)
- FACT-L and FACT-An Questionnaires

Vital signs should be obtained immediately before and after G1T28 or placebo, etoposide, and carboplatin infusions; only once between infusions.

In order to start Cycle 2 and subsequent cycles as scheduled, on Day 1 of the cycle, patients must have an ANC  $\geq 1.5 \times 10^9/L$ , platelet count  $\geq 100 \times 10^9/L$ , and nonhematologic drug-related toxicities (except alopecia) must be  $\leq$  Grade 1 or have returned to baseline. Dose modifications based on lack of recovery to these absolute neutrophil and platelet counts on the first day of treatment for Cycle 2 are outlined in [Table 8-2](#). A delay of up to 2 weeks is permitted to allow recovery from any toxicity in order to meet the continuation criteria for organ function. If the patient meets the criteria for starting the subsequent cycle as stated in protocol Section [6.1.3](#), a delay of up to 1 week is permitted for administrative reasons (eg, holiday, vacation, etc.). If a cycle is delayed, the patient should still complete the clinical laboratory assessments and the FACT-L and FACT-An questionnaires on the scheduled Day 1 of the next cycle, as well as the actual first dosing day of the next cycle of G1T28 or placebo + E/P therapy.

A patient will be discontinued from the study if recovery from any toxicity, in order to meet the continuation criteria for organ function, and any delay for administrative reasons requires a total delay of  $> 2$  weeks.

Study treatments (G1T28 or placebo + E/P chemotherapy) will be administered as described in Section [8.1](#).

#### Cycle 2 Days 2, 3, 8, 10, and 15

All procedures and assessments to be conducted during Cycle 2 Days 2, 3, 8, 10, and 15 are outlined in [Table 9-1](#). The DMC may recommend decreasing the frequency of hematological evaluations based on accumulating data. The investigators and IRBs will be notified if the frequency is reduced.

For Cycle 2 Day 2 and Day 3, study treatments (G1T28 or placebo + etoposide) will be administered as described in Section [8.1](#).

For tumor assessment, all sites of disease should be assessed radiologically by CT or MRI at screening and after every even cycle, until the occurrence of disease progression. CT or MRI scans obtained as standard of care prior to informed consent will not need to be repeated if performed within 14 days prior to dosing. Additional scans may be obtained at the discretion of the investigator, if clinically indicated. If a patient shows a radiological response (CR or PR), a confirmatory radiological assessment will be performed at least 4 weeks after the response was first noted. The same method of assessment (CT or MRI) should be used to characterize tumors at screening and at all follow-up assessments.

### **10.5. Cycles 3, 4, and Subsequent Cycles**

Procedures and assessments to be performed during Cycle 3 and all subsequent odd numbered cycles are similar to Cycle 1 (see Section [10.3](#) and [Table 9-1](#)).

Procedures and assessments to be performed during Cycle 4 and all subsequent even numbered cycles are similar to Cycle 2 (see Section [10.4](#) and [Table 9-1](#)).

In order to start each subsequent cycle as scheduled on the first day of the cycle, patients must have an ANC  $\geq 1.5 \times 10^9/L$ , platelet count  $\geq 100 \times 10^9/L$ , and nonhematologic

drug-related toxicities (except alopecia) must be  $\leq$  Grade 1 or have returned to baseline. Dose modifications based on lack of recovery to these absolute neutrophil and platelet counts on the first day of treatment for each subsequent cycle are outlined in [Table 8-2](#). A delay of up to 2 weeks is permitted to allow recovery from any toxicity in order to meet the continuation criteria for organ function. If the patient meets the criteria for starting the subsequent cycle as stated in protocol Section [6.1.3](#), a delay of up to 1 week is permitted for administrative reasons (eg, holiday, vacation, etc.). A patient will be discontinued from the study if recovery from any toxicity, in order to meet the continuation criteria for organ function, and any delay for administrative reasons requires a total delay of  $> 2$  weeks.

After discontinuation of study drug, patients should be strongly encouraged to complete all scheduled assessments through the end of their current 21-day treatment cycle, including the patient-reported outcome (PRO) scales; CBC assessment on Day 22; the Post-Treatment Visit; and the Survival Follow-up Phase of the study, which is to continue until at least 50% of randomized patients in Part 2 have died.

#### **10.6. Post-Treatment Visit**

Patients will return to the study center for a Post-Treatment Visit within 30 days from the last dose (+ 3 days). The following procedures will be performed at this visit:

- ECOG performance status evaluation
- Physical examination
- Weight and vital signs measurements
- Clinical chemistry, hematology, and urinalysis tests
- Electrocardiogram
- Tumor assessment (obtain tumor assessment by CT scan or MRI for patients who have not progressed at the time of study drug discontinuation [may be performed within 4 weeks]); see details in [Section 11.5.1](#))
- Brain scan with contrast (obtain brain scans by MRI or CT for patients who have not progressed at the time of study drug discontinuation [may be performed within 4 weeks])
- FACT-L and FACT-An Questionnaires
- Immunologic markers blood sample collection (**Part 2 only**)

For patients who have a confirmed CR, it is strongly recommended that they receive PCI after completion of chemotherapy. Patients with a confirmed partial response should also consider PCI after completion of chemotherapy based on the investigator's judgment.

After completing the Post-Treatment Visit, patients will enter the long-term Survival Follow-up Phase.

#### **10.7. Survival Follow-up Phase**

Monthly phone calls will be made to each patient that is in the long-term Survival Follow-up Phase. Patients will be followed for survival at a minimum until 50% of the patients randomized to Part 2 of the study have died. In addition, for patients who have not had disease progression at the time of study drug discontinuation, tumor assessments, including all sites of disease, will be assessed radiologically by CT or MRI, as performed at screening,

every 2 months (approximately  $60 \pm 7$  days) until the occurrence of progressive disease or study completion.

The following information will be collected monthly for all patients:

- Survival status
- Details of any anticancer treatment

The following additional information will be collected at  $60 \pm 7$  days after the Post-Treatment Visit (**Part 2 only**):

- Immunologic markers blood sample collection
- Hematology sample collection

### **10.8. Study Drug Discontinuation**

After discontinuation of study drug, patients should be strongly encouraged to complete all scheduled assessments through the end of their current 21-day treatment cycle, including the patient-reported outcome (PRO) scales; CBC assessment on Day 22; the Post-Treatment Visit; and the Survival Follow-up Phase of the study, which is to continue until at least 50% of randomized patients in Part 2 have died. Any abnormal results that are believed to be related to the study drug treatment should be repeated as often as deemed appropriate by the investigator until the abnormality resolves, returns to predose levels, or is otherwise explained.

### **10.9. Unscheduled Visits**

Additional visits can be performed as appropriate and at the discretion of the investigator.

## **11. STUDY ASSESSMENTS**

### **11.1. Efficacy Assessments**

Efficacy evaluation will be based on the following: kinetics of changes in CBCs; hematologic toxicities, including febrile neutropenia and infections; RBC and platelet transfusions; hematopoietic growth factor utilization; systemic antibiotic use; chemotherapy dose reductions and dose interruptions; alopecia; mucositis; nephrotoxicity; fatigue; and FACT-L and FACT-An. All of these variables, except for the PROs, will be assessed as described in the safety assessments (monitoring of AEs, clinical laboratory assessments, study treatment exposure, and concomitant medications) (see Section 11.3 and Table 9-1). PROs are described in Section 11.6.

The toxicity of G1T28 administered IV with E/P therapy will be assessed using the NCI CTCAE, Version 4.03.

### **11.2. Pharmacokinetic Assessments**

In the Phase 1b dose-finding portion of Part 1 of the study, serial blood samples (5-mL samples) will be collected for measurement of G1T28, etoposide, and carboplatin concentrations in plasma at the time points outlined below and in Table 9-1. Comprehensive information on blood sample acquisition, the specific type of collection tube with anticoagulant, and handling and storage are to be found in the Laboratory Manual. The analytical laboratory will measure plasma concentrations of G1T28, etoposide, and carboplatin using a validated method. Any remaining sample may be stored long term for the future analysis of G1T28 drug metabolites.

**Phase 1b Dose-Finding Portion of Part 1: Cycle 1 Day 1**

Blood samples will be collected at the following time points on Cycle 1 Day 1 for all patients enrolled in Cohort 1 of the Phase 1b dose-finding portion of Part 1 of the study: predose (0 hour; prior to dosing of G1T28) and at 0.5 (end of infusion [EOI] of G1T28), 1 (EOI of carboplatin), 1.5, 2 (EOI of etoposide), 2.5, 3, 4.5, 6.5, 8.5 (optional time point, if approved by the sponsor in advance), and 24.5 hours postdose (relative to the start of G1T28 infusion). Collection of PK blood samples in additional cohorts of the Phase 1b dose-finding portion of Part 1 is optional. The EOI sample for G1T28 should be drawn 2 to 5 minutes prior to the EOI. The EOI samples for G1T28, carboplatin, and etoposide must be drawn after completing infusion of the drugs and the actual times at which the samples were drawn should be documented. A  $\pm$  5-minute time window will be allowed for samples collected between the following time points: predose to 2.5 hours after the end of G1T28 infusion. A  $\pm$  10-minute time window will be allowed for samples collected between the following time points: 3 to 8.5 hours after the end of G1T28 infusion. A  $\pm$  1-hour time window will be allowed for the 24.5 hours after the end of G1T28 infusion time point. The actual time of blood sample collection should be documented in the eCRF. The Cycle 1 Day 1 sampling scheme is summarized in [Table 11-1](#).

**Table 11-1 Day 1 of Cycle 1 Blood Sampling Scheme Based on Predicted Administration Times of G1T28, Carboplatin, and Etoposide**

Sample	1	2	3	4	5	6	7	8	9	10	11
Sample Time (h)	0 (Predose a )	0.5 b (G1T28 EOI)	1 (Carbo EOI)	1.5	2 (Etop EOI)	2.5	3	4.5	6.5	8.5 (optional c )	24.5

Carbo = carboplatin; EOI = end of infusion; Etop = etoposide; h = hour

Times are approximate. For simplicity, assumptions were based on 0.5 hour increments. Actual times will be recorded and may vary from those listed here.

- a Predose is defined as prior to dosing of G1T28.
- b The EOI sample for G1T28 should be drawn 2 to 5 minutes prior to the EOI.
- c 8.5 hour sample (optional time point, if approved by the sponsor in advance)

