**Phase 1b Dose-Finding Portion of Part 1: Cycle 1 Day 3**

Blood samples will be collected at the following time points on Cycle 1 Day 3 for all Cohort 1 patients enrolled in the Phase 1b dose-finding portion of Part 1 of the study: predose (0 hour; prior to dosing of G1T28) and at 0.5 (EOI of G1T28), 1, 1.5 (EOI of etoposide), 2, 2.5, 3.5, 4.5, 6.5, 8.5 (optional time point, if approved by the sponsor in advance), and 24.5 hours postdose (relative to the start of G1T28 infusion). Collection of PK blood samples in additional cohorts of the Phase 1b dose-finding portion of Part 1 is optional. The EOI sample for G1T28 should be drawn 2 to 5 minutes prior to the EOI. The EOI samples for G1T28 and etoposide must be drawn after completing infusion of the drugs and the actual times at which the samples were drawn should be documented. Time window parameters noted above for Cycle 1 Day 1 also apply to Cycle 1 Day 3. The Cycle 1 Day 3 sampling scheme is summarized in [Table 11-2](#).

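### Protocol 11.2 requires the G1T28 end-of-infusion PK sample both before and after the infusion ends, so observed Cmax can mix two kinds of draw; two sampling windows are also ambiguous

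*Protocol*

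**What the plan says.** In Protocol section 11.2, the Cycle 1 Day 1 text states: "The EOI sample for G1T28 should be drawn 2 to 5 minutes prior to the EOI". The following sentence reads: "The EOI samples for G1T28, carboplatin, and etoposide must be drawn after completing infusion of the drugs". The Day 3 text repeats the first rule and then adds: "The EOI samples for G1T28 and etoposide must be drawn after completing infusion of the drugs". The synopsis (pharmacokinetics evaluation, Days 1 and 3) and footnote b of Tables 11-1 and 11-2 give only the rule to draw before EOI.

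Sample times are counted from the start of the G1T28 infusion. The windows are counted from its end: ±5 minutes from "predose to 2.5 hours after the end of G1T28 infusion", ±10 minutes for "3 to 8.5 hours after the end of G1T28 infusion", and ±1 hour, which "will be allowed for the 24.5 hours after the end of G1T28 infusion time point". Day 3 uses the same windows.

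Actual draw times are to be recorded. Table 11-3 defines Cmax as the observed peak. SAP section 6.2.10 leaves the PK analysis to a separate document.

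**The concern.** G1T28 is named in both EOI sentences, so a site cannot comply with both. The rule to draw before EOI is phrased as a recommendation and the rule to draw after it as an obligation, so either choice is defensible.

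The EOI draw largely determines Cmax. Protocol section 4.2 reports a Phase 1a median Tmax of 0.25 to 0.47 h and three-compartment elimination, and the next scheduled sample is at 1 h. If some patients are drawn on the rising limb and others on the falling limb, the summary of Cmax (a listed parameter under a secondary PK objective) combines values that are not like for like. Recorded times show which draw was taken, but they cannot supply a concentration that was not sampled. PK sampling is mandatory only for the 6 patients of Cohort 1, so a few such differences would be visible in the summary.

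The mismatch in time origin is a second, separate defect. It affects whether certain samples count as on time.

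**Working it through.** **1. Do the two EOI rules overlap?** The planned infusion lasts 30 minutes (Protocol 8.4.1, which also lets it run longer to empty the bag).
- Before-EOI rule: 30 − 5 = 25 to 30 − 2 = 28 minutes after the start.
- After-EOI rule: 30 minutes or later.
- The ranges do not overlap. The ±5-minute window around 0.5 h covers 25 to 35 minutes, so neither draw would be flagged as off-window.

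**2. How different are the two draws?** The documents give no early-phase half-life *h*, so *h* is assumed. The model is one compartment with a 30-minute constant infusion, each draw shown as a fraction of the level at exactly EOI:
- *d* minutes before EOI: (1 − 2^(−(30−d)/h)) / (1 − 2^(−30/h))
- *d* minutes after EOI: 2^(−d/h)

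For *d* = 5 and *h* = 10: before = (1 − 2^(−2.5)) / (1 − 2^(−3)) = 0.823/0.875 = 94.1%; after = 2^(−0.5) = 70.7%; ratio 70.7/94.1 = 0.75, so the later draw is 25% lower.

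| h (min) | 5 min before | 5 min after | after relative to before |
|---|---|---|---|
| 10 | 94.1% | 70.7% | −25% |
| 20 | 89.7% | 84.1% | −6% |
| 30 | 87.8% | 89.1% | +1% |

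With draws 2 minutes either side, the contrast is 97.9% against 87.1% (−11%) at *h* = 10, and 95.3% against 95.5% (about 0%) at *h* = 30. Outside the main range, 5-minute draws give 98.4% against 50.0% (−49%) at *h* = 5, and 85.6% against 94.4% (+10%) at *h* = 60. Both the size and the sign therefore depend on a half-life that the documents do not state.

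**3. Does this reach the dose rule?** Protocol 6.1.1.2 compares mean AUC0-24.5h with 3100 h·ng/mL ± 20%: 3100 × 0.8 = 2480 and 3100 × 1.2 = 3720, as the plan states. The illustration assumes a fast phase of 5 to 60 minutes plus a slow phase of 13.8 h (midpoint of the 12.9 to 14.7 h in section 4.2), with the slow phase weighted 2% or 10%. It uses linear-up/log-down trapezoids and actual draw times. Relative to a draw exactly at EOI:
- draws 2 to 5 minutes before EOI lower AUC by about 0 to 3%;
- draws 2 to 5 minutes after EOI lower it by about 1 to 12%.

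Even if every draw were late, the shift stays inside the 20% band width under these assumptions. A mix of draws gives something between the two cases.

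**4. What does the time origin change?** For a 30-minute infusion, time after end = time after start − 0.5 h.
- Day 1 3-h sample: 3 − 0.5 = 2.5 h after the end. Read from the start, its window is ±10 minutes; read from the end, ±5 minutes.
- 24.5-h sample (Days 1 and 3): read from the start, 23.5 to 25.5 h. Read from the end, the window is centred on 24.5 + 0.5 = 25 h after the start, so 24 to 26 h. No sample is scheduled at that centre.
- All other scheduled samples keep the same window width under either reading. Day 3 has no 3-h sample; its 3.5-h sample is 3.0 h after the end and keeps ±10 minutes.

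**The case against.** The case for treating this as minor is substantial. The before-EOI rule is specific to G1T28 and appears six times (twice in the synopsis, twice in the section 11.2 text, and in footnote b of both tables). The after-EOI rule appears twice, in sentences covering several drugs. Sites that simply followed the sampling tables would produce no mixing. Collection details are deferred to a Laboratory Manual that is not available here, the tables call their times approximate, and actual times are recorded. All of this stands, and it is why the claim is only that mixing can occur.

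Four stronger readings are tempting and are not supported.
- **That Cmax will be mixed.** This requires sites or patients to resolve the conflict differently, which the documents do not establish.
- **That the error is 11% to 29%.** Those figures (1 − 2^(−5/30) and 1 − 2^(−5/10)) compare a late draw with the level at exactly EOI. The before-EOI rule does not sample that level either. The relevant contrast is early draw against late draw, as in step 2. Setting a timing difference beside the Phase 1a between-patient CV of under 15% also does not show that any decision changes.
- **That the dose decision is compromised.** No numeric Cmax criterion appears in the dose rule, and the safety monitoring committee also weighs safety data.
- **That the time-origin mismatch distorts Cmax, or moves every window by half an hour.** The EOI sample has the same ±5-minute window under both origins.

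The contradiction itself survives. Nothing in the protocol or SAP says which sentence governs.

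**Conclusion.** The plan is wrong as written on a rule that sites must carry out: two adjacent sentences, on each of two days, cannot both be followed for the same G1T28 sample. The consequence is conditional. If practice varied, Cmax could differ systematically between draw types by about 25% at a 10-minute half-life and by almost nothing at 30 minutes, for draws 5 minutes either side of EOI. That range rests on an assumed one-compartment model with a 30-minute infusion, whereas the protocol reports three compartments.

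The effect on the AUC-based dose rule is indirect and probably small, although a mean close to an edge of the band could still be affected. The time-origin mismatch is real but limited to the Day 1 3-hour sample and the 24.5-hour samples. Scope is limited as well: PK is a secondary objective of the dose-finding portion, and sampling is optional after Cohort 1. This is an internal inconsistency that should be corrected; it does not show that the PK results are unreliable.

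**What to change.** - Reconcile the synopsis, the Day 1 and Day 3 text of section 11.2, and footnote b of Tables 11-1 and 11-2 into one instruction for the G1T28 EOI sample, stated separately from carboplatin and etoposide. The sponsor should decide which draw is intended.
- Use one time origin for nominal times and windows, and restate the windows for the Day 1 3-hour and the 24.5-hour samples accordingly.
- For samples already collected, use the recorded infusion and draw times to classify each G1T28 EOI draw as before or after EOI, and report the classification alongside Cmax in the separate PK analysis document. This matters because the footnote to SAP Table 9 shows that 200 and 240 mg/m² had already been evaluated in Part 1, so rewording cannot alter those data. Corrected wording still serves the further PK sampling that the synopsis allows in the expansion cohort and Part 2.

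The cost is wording in the protocol and Laboratory Manual, plus one classification variable in the PK analysis. No additional samples or patients are needed.
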